7 STUDY DESIGN

7.1 DESCRIPTION OF THE PROTOCOL

❖ Run-in

The 2-week run-in period consists of two visits: Visit 1 at Week -2 and Visit 2 at Week 0. Visit 1 and Visit 2 may be performed on the same day. During these visits, after having obtained signed informed consent from the patient, the Investigator will gather demographic and medical history data, perform a physical examination of the patients and evaluate their eligibility for the study according to inclusion/exclusion criteria indicated in [Section 8](#). Eligible patients will then be randomized in a 1:1 ratio into two treatment groups and will be dispensed one of the study treatments:

- Lertal® double-layer tablets (1 tab/day for 4 weeks) plus standard therapy (antihistamine).

or

- Lertal® placebo tablets (1 tab/day for 4 weeks) plus standard therapy (antihistamine).

The randomization list will be stratified by type of allergy (pollen or dust mites).

Baseline assessments of patient reported outcomes (PRO) will be collected at Visit 2 (Week 0). The patient will also be given a diary on which to record the use of rescue medication/concomitant medication and the occurrence of adverse events. The diary will also be used to record the occurrence/duration of exacerbations during Period II (need of an antihistamine medication of any kind, at any dose and of any duration).

❖ Period I

Visit 3 (Week 2) and Visit 4 (Week 4) constitute the 4-week double-blinded treatment period (Period I). During these visits, patients will be asked to complete their questionnaires and to return their diaries so information concerning safety (adverse events) and the use of rescue/concomitant medications can be collected. Patients need to return all unused product at both visits to check compliance with treatment. Once all data entry related to Period I has been completed (the Investigator has to certify that the data entered are complete and accurate), the eCRF will make the unblinding procedure available to the investigator so he or she can find out what treatment was

taken by the patient during the double-blinded period. All assessments scheduled for Visit 4 shall be performed prior to unblinding.

A patient that concludes treatment Period I and still presents symptoms that do not permit interruption of standard therapy is considered a non-responder and will not take part in Period II of the study. The patient will be discontinued from the study.

❖ Period II

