9.3 STANDARD TREATMENT

Standard therapy is an antihistamine chosen by the Investigator based on the clinical features of each patient and is to be used for 4 weeks (Period I) by patients of both treatment groups.

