11.2.2 Permanent treatment discontinuation

The patients may withdraw from treatment at any time and irrespective of the reason, or this may be the Investigator's decision. A patient that concludes treatment Period I and still presents symptoms that do not permit interruption of standard therapy is considered a *non-responder* and will be discontinued from the study. All efforts should be made to document the reasons for treatment discontinuation on the eCRF. Discontinued patients will not be replaced.

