13.2.2 Statistical Analysis

All data collected in the study will be listed and summarized as appropriate as described below. Continuous data will be summarized by means of common descriptive statistics: mean, standard deviation (SD), median, first and third quartiles, minimum and maximum. Categorical data will be presented by absolute and relative frequencies (n and %) or contingency tables.

For the safety analysis, patients will be included in based on available assessments; no missing data handling approach will be applied. For efficacy analyses, patients who interrupt treatment will be considered as “failures” for qualitative variables and their missing quantitative data will be substituted according to the LOCF method (Last Observation Carried Forward). Unless stated otherwise, two-sided p-values <0.05 will be considered statistically significant.

All statistical tables, listings, figures and analyses will be generated using SAS® release 9.4 or later (SAS Institute Inc., Cary NC, USA).

No interim analyses are planned.

Further details about data analysis will be provided in the Statistical Analysis Plan document.

All data about patient demographics and baseline characteristics will be summarized on the ITT population by treatment group by means of summary descriptive statistics.

The number and percentages of subjects meeting all eligibility criteria at screening will be provided. The analysis populations will be described and the reasons for excluding a patient from any particular population will be provided with the number of protocol deviators per each criterion.

A complete description of patients’ disposition will be provided specifying the number of randomized patients, the number of patients at each visit, the number of completed and discontinued patients and the reason for the discontinuation.

Medical history data will be presented by Medical Dictionary for Regulatory Activities MedDRA dictionary system organ class (SOC) and preferred term (PT).

Concomitant medications and significant non-drug therapies will be presented by WHO Drug Dictionary ATC class and preferred term.

- **Primary endpoint**

Changes from baseline of TSS scores will be calculated after 4 weeks of treatment. The between-group analysis will be performed by means of a t-test for independent samples or analogous non-parametric test.

- **Secondary endpoints**

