- Change from baseline of VAS score after 2 and 4 weeks of treatment. The between-group analysis will be performed by means of a t-test for independent samples or analogous non-parametric test.

- Changes from baseline of TSS scores after 2 weeks of treatment. The between-group analysis will be performed by means of a t-test for independent samples or analogous non-parametric test.
 - Changes from baseline of TSS score for each patient after 2 and 4 weeks of treatment will be classified as $\geq 30\%$ and $< 30\%$, thus defining responder and non-responder patients. Between-group differences will be tested by means of a Chi-square test with 2x2 contingency tables.
 - Time to maximum effect on TSS vs placebo will be analysed by means of t-test for independent samples after log-transformation of the data or analogous non-parametric test.
 - Between-group differences in the number of patients using rescue treatment will be analyzed by means of a Chi-square test with 2x2 contingency tables.
 - Changes from baseline in TNSS, TOSS and TTSS scores will be calculated after 2 and 4 weeks of treatment and between-group differences analyzed by means of a t-test for independent samples or analogous non-parametric test.
 - The number of patients with score for a single symptom ≤ 1 will be calculated and the between-group differences analyzed by means of a Chi-square test with 2xn contingency tables, where n represents the number of observations.
 - The intensity of the onset of exacerbations occurring during Period II will be evaluated through the TTS score and compared between the two groups using a t-test for independent samples or analogous non-parametric test.
 - The between-group differences in the number and duration of exacerbations occurring during Period II will be analyzed by means of a Mann-Whitney U test.
- **Quality of life**

Changes from baseline of the PRQLQ total score will be calculated at the end of Period I (Week 4) and end of Period II (Week 8 or Week16). An analysis of variance for repeated measures will be adopted, isolating the variability due to type of allergy, treatment group, time of observation and their interaction.

- **Safety**

All safety analyses will be performed on the Safety set. No missing data handling approach will be applied.

Results of physical examinations at each assessment will be presented.

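### The PRQLQ model names no Week 4 contrast, and its treatment main effect averages a blinded comparison with an open-label one in selected patients

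*Combined protocol and SAP*

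**What the plan says.** The quality-of-life paragraph of Section 13.2.2, repeated in the synopsis, takes PRQLQ change "calculated at the end of Period I (Week 4) and end of Period II (Week 8 or Week16", the later visit being Week 8 for pollen and Week 16 for mite patients. Both time points go into one model: "An analysis of variance for repeated measures will be adopted, isolating the variability due to type of allergy, treatment group, time of observation", and the sentence ends by adding the interaction of these factors. No term or contrast is named as the quality-of-life result.

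The two time points come from different settings. For Period I, Section 9.3 says the antihistamine "is to be used for 4 weeks (Period I) by patients of both treatment groups", and Section 7.1 says "All assessments scheduled for Visit 4 shall be performed prior to unblinding". In Period II (Sections 7.1, 9.1 and 9.2) the active arm takes Lertal without standard therapy, the control arm takes nothing, and treatment is open-label. A patient whose symptoms at the end of Period I do not allow standard therapy to stop does not enter Period II and, under Section 11.2.2, "will be discontinued from the study". Section 11.2.3, however, has patients followed to the scheduled end of the study after permanent treatment discontinuation.

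For efficacy data of patients who interrupt treatment, Sections 13.2.1 and 13.2.2 state that "their missing quantitative data will be substituted according to the LOCF method".

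**The concern.** Week 4 PRQLQ is a randomised, blinded comparison in the whole trial population. The end-of-Period-II value answers another question, without blinding, in patients chosen by an outcome that treatment may have affected. If the treatment main effect of the joint model is reported as the quality-of-life result, a difference that arises only in the open-label period can be read as a blinded benefit, and a real Week 4 benefit can be diluted.

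The model also needs a rule for patients who have a Week 4 value and no Period II value. The written rule covers patients who interrupt treatment. Non-responders are described as having concluded Period I, and control patients have no study treatment to interrupt in Period II. The rule may cover these patients or may not, and the consequence differs.

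**Working it through.** **1. The plan's own figure.** The only sample-size calculation (Section 13.1) is for TSS: n = 2(z₀.₉₇₅ + z₀.₈₀)²/d² = 2(1.960 + 0.842)²/0.47² = 71.1, so 72 per group. Exact t-test power at 72 is 0.7998, so the figure reproduces. Allowing for 12% dropout, 72/0.88 = 81.8, against 80 stated, which is close. Nothing is stated for PRQLQ. Below, 0.47 SD and 72 per group only set a scale.

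**2. The two contrasts.**

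| | Week 4 | End of Period II |
|---|---|---|
| Comparison | Lertal + antihistamine vs placebo + antihistamine | Lertal alone vs no treatment |
| Blinding | Double-blind | Open-label |
| Patients | All with a Week 4 value | Those able to stop standard therapy |
| Week | 4 | 8 (pollen), 16 (mite) |

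**3. Main effect.** Let δ₄ and δ_II be the two effects, positive favouring Lertal. With balanced data the treatment main effect is (δ₄ + δ_II)/2. For (0, 0.47) and for (0.47, 0) it is 0.235, so it cannot tell the two cases apart. With unit SDs and between-visit correlation ρ, a patient's two-visit mean has SD √((1 + ρ)/2). At ρ = 0.6 this is 0.894, the standardised effect is 0.235/0.894 = 0.263, and the noncentrality at 72 per group is 0.263 × √36 = 1.58. Power is about 35%; it is 39% at ρ = 0.4 and 32% at ρ = 0.8. In the (0, 0.47) case, that is how often the main effect is significant with no Week 4 effect at all.

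**4. Interaction.** Treatment-by-time tests δ_II − δ₄. For a difference of 0.47 its power is 73%, 88% and 99% at ρ = 0.4, 0.6 and 0.8. It shows whether the effects differ. Effects of (0, 0) and (0.47, 0.47) both give zero, so it does not say whether Lertal improves PRQLQ at Week 4.

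**5. Non-responders.** Simulation: 80 per arm, 1,500 runs, between-visit correlation 0.6, and removal at Week 4 on a symptom score correlated 0.6 with PRQLQ. The symptom effect equals the Week 4 PRQLQ effect, except in row 2. The share is the average over both arms; at 20% with a symptom effect of 0.47 it is about 26% on placebo and 14% on Lertal. Shares and correlations are assumptions.

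| Estimate (SD) | 10% | 20% | 30% | 40% |
|---|---|---|---|---|
| Incomplete cases dropped: Week 4, truth 0.47 | 0.39 | 0.36 | 0.32–0.33 | 0.30 |
| Incomplete cases dropped: Week 4, truth 0, symptom effect 0.47 | −0.08 | −0.11 | −0.14 | −0.16 |
| LOCF: Week 4, truth 0.47 | 0.47 | 0.47 | 0.46–0.47 | 0.47 |
| LOCF: Period II, truth 0, Week 4 effect 0.47 | 0.06 | 0.09 | 0.12 | 0.16 |
| LOCF: Period II, truth 0.47, Week 4 effect 0 | 0.43 | 0.38 | 0.34 | 0.28 |
| LOCF: Period II, truth 0.47, Week 4 effect 0.47 | 0.50 | 0.50 | 0.48 | 0.48 |

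Row 5 can be checked by hand. With equal shares f in both arms, LOCF gives (1 − f) × 0.47 = 0.42, 0.38, 0.33, 0.28. A likelihood-based model using all data also left the Week 4 estimate at about 0.46–0.47.

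**6. Time and allergy type.** Randomisation is stratified by allergy type (Section 9.4), and within a stratum both arms share the same late visit. The week difference therefore does not bias the treatment comparison within strata. It does prevent a time effect from being separated from an allergy effect. The time levels are themselves unclear: the assessment chart and Section 11.1 list PRQLQ at both Visit 5 and Visit 6, while Section 10.1.4 says one or the other.

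**The case against.** The strongest reply is that the model contains the interaction, that change is calculated at each time point, and that no sentence makes the main effect the quality-of-life result. That stands in part. A reader might infer that the model cannot separate the two periods; the documents do not support this, because treatment-by-time can do so. What is missing is a named Week 4 contrast.

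The second reply is that LOCF is the stated rule and that Section 11.2.2 treats non-responders under permanent treatment discontinuation, so it is natural to read LOCF as covering them. A reader might infer that Period II drop-outs distort the Week 4 result. That requires incomplete cases to be dropped, which no section specifies. Under LOCF the Week 4 estimate is unchanged and the alteration falls on Period II. Nor is it certain that non-responders lack Period II values, given Section 11.2.3.

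Third, PRQLQ is one of many secondary endpoints, it does not drive the sample size, and Section 13.2.2 defers detail to a separate analysis plan. This limits the weight of the point, and it also means that the gap can be closed there.

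**Conclusion.** The concern holds as a gap in specification. One model spans two different treatment comparisons, its main effect is their average, and no Week 4 contrast is named. An open-label effect of 0.47 SD with nothing at Week 4 gives a main effect of 0.235 SD, significant in 32–39% of trials at 72 per group for correlations of 0.8 to 0.4.

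The missing-data consequence is conditional. If LOCF covers non-responders at assumed shares of 10–40%, a true Period II effect of 0 becomes about 0.06–0.16 SD when the Week 4 effect is 0.47, and a true 0.47 becomes about 0.43–0.28 SD when the Week 4 effect is 0. When both effects are 0.47, LOCF changes little. Only if incomplete cases are dropped does the Week 4 effect itself shrink, from 0.47 to about 0.36–0.30 SD at 20–40%, a loss of 23–36%.

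The averaging of the two contrasts follows from the documents. The sizes rest on assumed effects, correlations and non-responder shares. The primary TSS analysis is not affected.

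**What to change.** In the analysis plan:

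- Make PRQLQ change at Week 4, in all ITT patients, the inferential quality-of-life analysis, by ANCOVA with treatment, baseline PRQLQ and allergy type. A named Week 4 contrast would already end the ambiguity; a stand-alone analysis also keeps Week 4 valid however Period II gaps are handled.
- State how an ITT patient with no Week 4 PRQLQ is handled, since ITT membership rests on the primary variable.
- Report Period II PRQLQ separately by allergy type at the actual week, as estimates with confidence intervals, labelled as open-label in a selected subset, and without carrying forward Week 4 scores obtained on antihistamine.
- State whether LOCF applies to Week 4 non-responders and to control patients who leave Period II.
- Reconcile Section 11.2.3 with Sections 7.1 and 11.2.2 on follow-up, and Section 10.1.4 with the assessment chart and Section 11.1 on the Period II PRQLQ visits.

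The cost is wording. Baseline PRQLQ and allergy type are already collected. The pooled quality-of-life test is given up, and Period II PRQLQ becomes descriptive.

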9.2 PLACEBO

One placebo tablet identical in appearance, size and taste to Lertal[®] tablets is to be administered daily together with standard therapy (antihistamine) by patients randomized to the placebo + standard treatment group for 4 weeks (Period I only). In Period II, patients taking placebo tablets in Period 1 receive no further treatment.

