13.1 DETERMINATION OF SAMPLE SIZE

160 patients are to be enrolled in this study.

Confidential

A sample of 72 patients for each group will have an 80% power to detect an effect size on the primary variable ($\delta = |\mu_1 - \mu_2| / \sigma$) of 0.47 (medium effect size) (12), using an independent samples t-test with a two-tailed significance level of 5%.

A sample size of 80 patients per group will account for an expected dropout rate of 12% (13), using Freedman's formula (*Control Clin Trials*, 1990): $n' = 100 * n / 100 - x$, where x is the expected dropout rate.

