The incidence of Adverse Events (AEs) and Serious Adverse Events (SAEs) recorded throughout the study will be presented overall and by treatment group respectively.

According to the onset date of the event, AEs will be defined as follows:

- treatment-emergent AE, those events with an onset date after any treatment initiation
- non-treatment-emergent AE, those events with an onset date between informed consent and any treatment initiation

Nontreatment-emergent AEs will be listed only.

Treatment-emergent AEs will be summarized by MedDRA dictionary system organ class and preferred term. A summary of treatment-emergent AEs by preferred term and severity will be also provided. All related treatment-emergent AEs, treatment-emergent AEs with an outcome of death, treatment-emergent AEs leading to discontinuation of treatment will be summarized by MedDRA dictionary system organ class and preferred term and will also be listed. Serious treatment-emergent AEs will be summarized similarly.

All deaths occurred will be listed together with all their details.

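### Adverse events are to be tabulated by arm over the whole study, with no separate table for the blinded Period I and no end to the treatment-emergent window; the window for the rescue test is unstated

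*Combined protocol and SAP*

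**What the plan says.** **Adverse events.** Section 13.2.2 (Safety) plans that AEs and SAEs "recorded throughout the study will be presented overall and by treatment group respectively". The sentence is awkward, but Section 13.2.1 confirms that safety is reported overall and by actual treatment group. The class on which the summaries rest is "treatment-emergent AE, those events with an onset date after any treatment initiation". No end of window, period or person-time denominator is given. The summaries by organ class and preferred term, by severity, of related events, of events leading to discontinuation and of serious events all use this class.

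**Design.** Period I is four weeks, double-blind, Lertal against placebo, both with an antihistamine (Section 7.1). Period II is open-label and lasts 4 weeks for pollen or 12 weeks for mite allergy. Section 9.2 adds: "In Period II, patients taking placebo tablets in Period 1 receive no further treatment". A patient whose symptoms do not allow standard therapy to stop does not enter Period II and is discontinued from the study (Sections 7.1 and 11.2.2). Section 11.2.3, however, follows patients after permanent treatment discontinuation up to scheduled completion.

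**Rescue.** Section 13.2.2 says: "Between-group differences in the number of patients using rescue treatment will be analyzed by means of a Chi-square test with 2x2 contingency tables". It names no time point or period. Section 9.10 defines rescue as a step-up of the antihistamine in Period I and as any antihistamine in Period II. Section 10.1.5 collects it in both.

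**The concern.** Period I is the only blinded, placebo-controlled safety comparison in the trial. At Week 4 four things change together: the comparator goes from placebo to nothing, patients and investigators can know the arm while AEs are still self-recorded in a diary, patients leave on the basis of an outcome that treatment may affect, and the length of follow-up comes to depend on allergy type. A by-arm percentage over both periods cannot be read as the safety of Lertal added to standard therapy, because for much of the time neither arm is on that regimen and the control arm takes no tablet.

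If more patients of one arm enter Period II, and those who do not enter are no longer observed, that arm also has more time in which to report an event. The two columns would then differ even if the product had no effect on AEs.

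For rescue, the two definitions describe different events. A single test across both periods would combine them, and would count Period II antihistamine use a second time, since the same use defines an exacerbation (Section 6.2).

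**Working it through.** **The plan's own figure.** The plan gives no AE rate, rescue rate or non-responder rate. Its only calculation is the sample size. For an effect of 0.47, two-sided 5% and 80% power, the normal formula 2(1.960 + 0.842)²/0.47² gives 71.1, so 72 per group; the exact t-test power at 72 is 79.98%. The stated 72 reproduces. Nothing below changes it.

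**Inputs.**
- From the documents: Period I is 4 weeks; total time from first dose is 8 weeks (pollen) or 16 weeks (mite) for those who enter Period II; 80 enrolled per arm.
- Assumed: mite share 60% (the enrolment block in Section 9.4 is the only guide); a constant AE hazard λ per week, equal in both arms, in both periods and in responders and non-responders; non-responder proportion nr by arm; non-responders not observed after Week 4.

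**Time at risk.** Mean Period II length for entrants is 0.6 × 12 + 0.4 × 4 = 8.8 weeks, so mean follow-up is 4 + (1 − nr) × 8.8.
- nr = 0.20: 4 + 0.80 × 8.8 = 11.0 weeks, of which 64% falls in Period II.
- nr = 0.40: 4 + 0.60 × 8.8 = 9.3 weeks, of which 57% falls in Period II.

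**Incidence.** nr(1 − e^(−4λ)) + (1 − nr)[0.6(1 − e^(−16λ)) + 0.4(1 − e^(−8λ))].

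At λ = 0.03 the 4-, 8- and 16-week incidences are 0.113, 0.213 and 0.381. Entrants have 0.6 × 0.381 + 0.4 × 0.213 = 0.314. The gap is then (0.314 − 0.113) = 0.201 times the difference in nr.

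| nr, Lertal / placebo | Whole study, Lertal | Whole study, placebo | Gap (points) | Period I, each arm |
|---|---|---|---|---|
| 20% / 20% | 27.4% | 27.4% | 0 | 11.3% |
| 20% / 25% | 27.4% | 26.4% | 1.0 | 11.3% |
| 20% / 40% | 27.4% | 23.4% | 4.0 | 11.3% |
| 20% / 60% | 27.4% | 19.3% | 8.0 | 11.3% |
| any split, all followed to the end | 31.4% | 31.4% | 0 | 11.3% |

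With 20% / 40% and other hazards:
- λ = 0.02 gives 19.4% against 16.5% (2.9 points).
- λ = 0.05 gives 40.6% against 35.0% (5.6 points).

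Swapping the two non-responder proportions reverses the sign.

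**Rescue, if it were pooled.** Assume equal risks in both arms (r1 in Period I, r2 among entrants in Period II), with 70% (Lertal) and 50% (placebo) entering. Pooled use is 1 − (1 − r1)(1 − entry × r2).
- r1 = 10%, r2 = 30%: 28.9% against 23.5%.
- r1 = 20%, r2 = 50%: 48.0% against 40.0%.

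Over r1 of 10–20% and r2 of 30–50%, the test at 80 per arm would reject in about 9–22% of trials instead of 5%, with no difference within either period. With equal entry it stays at 5%.

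**The case against.** **The AE tables are descriptive.** This stands. No test or safety hypothesis is planned. But by-arm incidence is the trial's safety result, and readers will set the columns side by side.

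**The period split may be in a separate document.** Section 13.2.2 defers further detail to a Statistical Analysis Plan and says that all data will be listed. A reader might infer that Period I safety will never be shown alone. The documents do not support that: the supplied text only fails to specify it. Still, its stated rule is whole-study presentation.

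**Follow-up may be equal.** If Section 11.2.3 covers non-responders, the exposure gap is zero. Sections 7.1 and 11.2.2 point the other way. The conflict is real, so unequal time at risk is conditional.

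**The size is assumed.** This stands. On a normal scale, 20% against 40% non-response is a shift of 0.842 − 0.253 = 0.59 SD, above the design effect of 0.47. The standard error of 27.4% − 23.4% at 80 per arm is √(0.274 × 0.726/80 + 0.234 × 0.766/80) = 6.9 points, so a 4-point gap is about 0.6 standard errors. In that scenario it also runs against Lertal and would not hide harm.

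**Rescue.** A reader might infer that one whole-study table is planned. The text does not say so. It refers to tables in the plural, with the same phrase used for responders at 2 and 4 weeks, and Period II antihistamine use has its own exacerbation analysis. The direction of any pooled bias is also open: Sections 13.2.1 and 13.2.2 count patients who interrupt treatment as failures, which, if applied to non-responders, could offset or reverse it. What remains is an unstated window, where the neighbouring TSS, VAS and responder items give time points and the exacerbation items name Period II.

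**Conclusion.** The AE point holds. The planned by-arm tables mix blinded Lertal against placebo with open-label Lertal against no treatment in a selected group, with no end of window and no exposure adjustment, and the supplied text specifies no Period I safety table by arm. This rests on the text and needs no assumed rate. It remains even if follow-up is equal, because the comparator and the blinding still change.

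The numerical distortion is conditional. It requires different entry into Period II and non-responders not followed. At 0.03 per week and 60% mite patients it is about 0.2 points for each point of difference in non-response: 4 points at 20% against 40%, 1 point at a 5-point difference, and zero with equal entry or full follow-up. A fixed 3-to-6-point bias should not be inferred.

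For rescue, the finding is an unstated window. Pooling is possible but not planned in the text.

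**What to change.** 1. Tabulate AEs and SAEs by arm for Period I, in all treated patients, as the main safety comparison.
2. Tabulate Period II separately as Lertal against no treatment, by allergy type, with patient-weeks at risk and events per patient-week, and label it open-label and selected.
3. Define the end of the treatment-emergent window on the same basis in both arms, and assign events to a period by onset date.
4. Keep the whole-study table as supplementary, since it shows cumulative experience over 8 to 16 weeks.
5. Reconcile Sections 7.1 and 11.2.2 (non-responders discontinued from the study) with Section 11.2.3 (follow-up to scheduled completion), so that time at risk is known.
6. State that the rescue chi-square test covers Period I, and report Period II antihistamine use under exacerbations.

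The cost is a few more tables. Onset dates already classify the AEs and the diary already records rescue use, so no patients, visits or alpha are needed. If a separate analysis plan already contains the split, a cross-reference is enough.
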